**Overview of Study Design and Key Features**

VISIT 2 (telephone call)

- GP reviews urinalysis and PSA lab results.
- Call subject: If lab results show NO probable BPH, then subject will not continue in the study. If PSA lab results show PROBABLE BPH ( $\geq 2$  ng/mL), subject proceeds to Part II and Visit 3 is scheduled for the urologist assessment.

Overview of Study Design and Key Features	

VISIT 3 (Part II – urologist clinic visit)
 
 
• Urologist reviews medical history and symptoms
 
• Brief physical examination
 
• DRE
 
• Review previous tests (BPE/BPO screening tool, IPSS screening tool, urinalysis, PSA)
 
 
↓
 
 
Urologist provides:
 
 
• Confirmation of clinical diagnosis of BPH (or confirmation the subject does NOT have BPH).
 
• Estimate whether the patient is at risk of progression of BPH (PSA<math>\geq</math>2.0ng/mL and other tests).
 
 
 
 
• NOTE: Urologist may need to perform additional diagnostic testing as per standard of care and as needed to assess the BPH diagnosis. This follow-up is not prescribed by this protocol, however, any data collected that is used for the final diagnosis will be entered in the study case report form (CRF). Advice or treatment post study will be discretion of the GP or Urologist.
 
	

Design Features
	
 
• No investigational study drug is being administered during this study.
 
• This is a non-randomized, interventional study utilizing a questionnaire-based assessment of men in General Practice. Men who sign the informed consent form and meet the eligibility criteria will be enrolled and complete the Part I diagnostic tests at the GP clinic. If the GP determines that the subject has probable BPH, the subject proceeds to Part II and is scheduled for a Urologist assessment and diagnostic tests to confirm or refute a BPH diagnosis and to assess the risk of progression of BPH.
 

Overview of Study Design and Key Features	
Dosing	
 
No investigational study drug is being administered during this study.
 

Treatment Assignment	
 
Subjects are not randomized or dispensed study treatment.
 
Approximately 1,500 males presenting to a GP with a primary complaint other than LUTS will be screened for probable BPH to yield 500 subjects being referred to a Urologist.
 

Interim Analysis	
 
No interim analyses are planned for this study.
 

## **2.4. Statistical Hypotheses**

The primary endpoint is defined as the proportion of men confirmed to have BPH based on full Urologist diagnostic testing in men with a positive result on the BPE/BPO screening tool and a probable BPH assessment by GP. Primary endpoint summaries will be descriptively presented in terms of the calculated proportion, described below, and a 95% confidence interval on the proportion. Formal hypothesis testing will not be conducted in terms of the primary and secondary endpoint proportions.

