## Analysis

- The primary endpoint is defined as the proportion of men that are confirmed to have BPH based on full urologist assessment of diagnostic test results among men with a positive result on the BPE/BPO screening tool and probable BPH diagnosis as assessed by the GP. For this proportion, the numerator is number of subjects diagnosed with BPH by a urologist; denominator is number of subjects with a positive result on the BPE/BPO screening tool and a probable BPH assessment by

the GP and a BPH assessment by the urologist. The 95% confidence interval for this proportion will be presented.

- Sufficient general practice centres (50 consecutive men per centre) in various markets will be recruited to administer the BPE/BPO screening tool to 1,500 men (using protocol defined criteria) presenting to clinic for reasons unrelated to the study. It is expected that 33% of the 1,500 presenting (or approximately 500) will have a positive result on the BPE/BPO screening tool and a probable BPH assessment by GP and thus will be assessed by a urologist.
- Due to the design of the study and types of endpoints incorporated, ‘observed cases’ will be summarized for a subset of subjects in study Parts I and II. There will be no imputations for missing data or for discontinued subjects.
- An interim analysis is not planned for this study.

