#### 4.1. Overall Design

This study is intended to reproduce the circumstances in which the BPH quick tool will be used in General Practice, i.e., in men that may have ‘hidden’ LUTS symptoms. To reproduce these circumstances of opportunistic screening, men will not be invited to attend their GP but **must attend spontaneously with for reasons that are not related to this study**. At this point they will be invited to participate in the study.

GPs participating in the study will recruit men  $\geq 50$  years that present in their clinic for reasons that are not related to this study.

After obtaining informed consent, the GP will initially assess all inclusion and exclusion criteria except for the questionnaire inclusion criterion. If the subject meets those eligibility requirements, the GP administers the BPE/BPO and IPSS screening tools. Subjects who have a positive score on the BPE/BPO screening tool (total score  $\geq 3$ ) and/or the IPSS tool (score  $\geq 8$ ) and meet all other eligibility requirements will be enrolled in Part I of the study. The GP then performs the following diagnostic tests for Part I of the study: urinalysis (sample sent to local lab if the strip test is positive) and Prostate Specific Antigen (PSA) blood test. If the serum PSA result is  $\geq 2$  ng/mL, the GP will make a diagnosis of ‘probable BPH (subjects with symptoms likely to be related to BPH)’ or not. All men with ‘probable BPH’ will proceed to Part II and will be scheduled for Visit 3 with a urologist for confirmation of the GP’s findings plus a brief physical exam and DRE. Additional testing may be performed as per standard of care to assist with a confirmatory diagnosis such as a DRE, however this is not required by the protocol.

The urologist is to:

1) Establish a clinical diagnosis of BPH

AND

2) Estimate whether the patient is at risk of progression of BPH (PSA  $\geq 2.0$  ng/mL and other testing).

For the purposes of this study the diagnosis of the urologist (BPH yes/no) is the operational definition of confirmed BPH. Those men refusing referral to the urologist, but considered by a GP to have BPH (after the tests specified above) will be classified as ‘probable BPH’.

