### **8.4.2. Primary Analyses**

The primary endpoint is defined as the proportion of men confirmed to have BPH based on full urologist diagnostic testing among men with a positive result on the BPE/BPO screening tool (score  $\geq 3$ ) and serum PSA  $\geq 2$  ng/mL. Primary endpoint summaries will be descriptively presented in terms of the calculated proportion, described below, and 95% confidence interval on the proportion. Formal hypothesis testing will not be conducted.

| Tool        | Proportion  | Numerator  | Denominator  |
|-------------|---|--|--|
| BPE/
BPO | BPH Diagnosis by Urologist based upon BPE/BPO screening tool (score $\geq 3$ ) and serum PSA $\geq 2$ ng/mL | Number of subjects diagnosed with BPH based on full urologist diagnostic testing | Number of subjects with a positive result on the BPE/BPO screening tool (score $\geq 3$ ) and serum PSA $\geq 2$ ng/mL and a BPH assessment by urologist |

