Evaluable	
 
Comprised of all subjects who meet the entry criteria, including a positive IPSS screening result (score <math>\geq 8</math>) and/or a positive BPE/BPO screening result (score <math>\geq 3</math>).
 
																			
Hypothesis	
 
The primary endpoint is defined as the proportion of men confirmed to have BPH based on full Urologist diagnostic testing in men with a positive result on the BPE/BPO screening tool (score <math>\geq 3</math>) and a serum PSA <math>\geq 2</math> ng/mL. Formal hypothesis testing will not be conducted in terms of the primary and secondary endpoint proportions.
 
																			

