**7.1.2. Planned Primary Efficacy Statistical Analyses**

Primary Statistical Analyses			
Endpoint(s)			

 
Proportion of men that are confirmed to have BPH based on full Urologist assessment of diagnostic test results among men with a positive result on the BPE/BPO screening tool (score <math>\geq 3</math>) and serum PSA <math>\geq 2</math> ng/mL.
 
Primary endpoint summaries will be descriptively presented in terms of the calculated proportion, described below, and 95% confidence interval on the proportion. Formal hypothesis testing will not be conducted.
 
			
Tool	Proportion	Numerator	Denominator
BPE/BPO	BPH diagnosis by Urologist based upon BPE/BPO screening tool (score $\geq 3$ ) and serum PSA $\geq 2$ ng/mL.	Number of subjects diagnosed with BPH based upon a BPH assessment by Urologist.	Number of subjects with a positive result on the BPE/BPO screening tool (score $\geq 3$ ) and serum PSA $\geq 2$ ng/mL and a BPH assessment by Urologist.

 
Table 3 provides an overview of the planned summaries and primary efficacy analyses. A list of planned data displays is in Appendix 15: List of Data Displays.
 
			
Model Specification			

 
No models were used during the statistical analysis; proportions and confidence intervals were computed.
 
			
Model Checking & Diagnostics			

 
Not Applicable
 
			
Model Results Presentation			

 
Not Applicable
 
			
Sensitivity and Supportive Statistical Analyses			

 
Not Applicable
 
			

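### The referral text conflicts on whether a GP can keep a tool-positive, PSA ≥2 man from the urologist, and the observed-case primary has no planned bound for men left unassessed

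*SAP*

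**What the plan says.** **Primary analysis.** The objective in both documents is the utility of the BPE/BPO tool together with PSA. The operative denominator is men with BPE/BPO ≥3 and PSA ≥2 "ng/mL and a BPH assessment by urologist" (Protocol 8.4.2). SAP 7.1.2 has the same ("ng/mL and a BPH assessment by Urologist"), and the SAP synopsis agrees. Observed cases are used, with no imputation for men who withdraw or do not qualify for the next part (Protocol 8.3.1, SAP 11.7.2). In SAP 7.1.2 the entry "Sensitivity and Supportive Statistical Analyses" is marked Not Applicable.

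**Leftover definitions.** Three places define the primary by GP diagnosis instead of PSA:
- the Protocol synopsis, Analysis: "denominator is number of subjects with a positive result on the BPE/BPO screening tool and a probable BPH assessment by" the GP;
- Protocol 8.1 and SAP 2.4: "in men with a positive result on the BPE/BPO screening tool and a probable BPH assessment by GP".

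The Hypothesis row of the SAP synopsis starts with similar words, "in men with a positive result on the BPE/BPO screening tool (score" ≥3), but goes on to PSA ≥2. The progression-risk endpoint in Protocol 3 has the same GP-based leftover, while Protocol 8.4.3 uses PSA ≥2.

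**Referral.** Protocol 4 spells out probable BPH as a positive questionnaire with PSA ≥2 and sends such men to Part II. Visit 2 in Protocol 4.1 and in SAP 2.3 likewise reads PSA ≥2 as probable BPH. The body of Protocol 4.1, however, says that when PSA is ≥2 "the GP will make a diagnosis of ‘probable BPH (subjects with symptoms likely to be related to BPH)’ or not". The synopsis asks the GP to judge whether the findings point to BPH rather than another cause, and the footnote in SAP 2.2 defines probable BPH without a PSA threshold. Only men with probable BPH are booked for Visit 3 (Protocol 6.1, footnote 4). Protocol 4.1 also foresees non-attendance: "Those men refusing referral to the urologist, but considered by a GP to have BPH" keep the probable label.

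**The concern.** If every man with BPE/BPO ≥3 and PSA ≥2 is referred and attends, the reported proportion answers the objective. If a GP may decline to refer some of them, those men never enter the denominator, and the figure describes tool plus PSA plus GP judgement under a label that mentions only tool and PSA. Men who refuse or miss the visit also drop out, for a different reason.

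The two losses need not act alike. If a GP's no carries information about BPH, the observed proportion would probably be too high for tool plus PSA alone. For men who refuse or do not attend, the direction is unknown. The stated precision covers neither loss.

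**Working it through.** **1. The plan's own precision.** Protocol 8.2 assumes p = 0.50 and a 95% interval. Half-width = 1.96 × √(p(1−p)/n):
- n = 300: 0.0566 (stated ±0.057)
- n = 500: 0.0438 (stated ±0.044)
- n = 700: 0.0370 (stated ±0.037)

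All three reproduce. They describe sampling error only.

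**2. Do the two denominators differ?** Protocol 4, 4.1 and Visit 2 make PSA ≥2 a condition for probable BPH, and only men with probable BPH go to the urologist. Among assessed men the definitions therefore differ only for those off the pathway, such as a GP yes at PSA <2.

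**3. What the planned displays give.** Within the BPE/BPO ≥3 category (SAP 6.1, 6.2 and 8.2.6), let A = men with PSA ≥2, B = GP yes, C = GP yes with a urologist assessment. If GP yes requires PSA ≥2:
- A − B = not referred (GP no, or no GP answer)
- B − C = referred but not assessed

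A minus the Table 2.13 denominator gives all unassessed men. Tables 2.49–2.51 count losses before the GP assessment, Tables 2.52–2.54 losses before the urologist visit (defined in SAP 8.1.2 among GP-yes men), and Tables 1.11–1.13 withdrawals by reason and visit. Tables 3.23–3.25 summarise PSA by GP answer: the minimum among GP-yes men tests the assumption above, and the maximum among GP-no men shows whether any had PSA ≥2. No listed table directly crosses PSA ≥2 with the GP answer among BPE/BPO ≥3 men, which would separate GP no from no answer. None bounds the primary. This is judged from the SAP text and table titles; the shells are filed separately (SAP 11.16).

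**4. Bounds.** Let u = the share of BPE/BPO ≥3, PSA ≥2 men without a urologist assessment (not in the documents; assumed). Lower = p(1−u); upper = p(1−u) + u; width = u. At p = 0.50:
- u = 0: no effect
- u = 5%: 0.475 to 0.525
- u = 10%: 0.45 to 0.55
- u = 20%: 0.40 to 0.60

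The worst-case shift p × u equals the half-width at u = 0.0438/0.50 = 0.088, that is 500 × 0.088/0.912 ≈ 48 men beside 500 assessed. Check: 250/548 = 0.456 and 298/548 = 0.544. The same step gives 38 men (11.3%) beside 300 and 56 (7.4%) beside 700.

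**5. Another p from the documents.** Sensitivity 83.8% and specificity 74.0% (Protocol 4.4) with prevalence 40–60% (Protocol 2.1):
- 40%: 0.838 × 0.40 / (0.838 × 0.40 + 0.26 × 0.60) = 0.682
- 60%: 0.838 × 0.60 / (0.838 × 0.60 + 0.26 × 0.40) = 0.829

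At u = 10% the bounds are 0.61–0.71 and 0.75–0.85. With 500 assessed, the half-widths are 0.0408 and 0.0330, reached in the worst case at u = 6.0% (32 men) and 4.0% (21 men). This assumes that the urology-setting accuracy transfers, and that the general prevalence applies to a sample that excludes men already tested or treated for BPH (Protocol 5.2).

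**The case against.** The strongest reply is that most of this is already visible. The denominator openly requires a urologist assessment, observed-case handling is prespecified, and the study is descriptive with no test of the primary. The attrition tables let a reader separate non-referral from non-attendance approximately by subtraction. Exclusion criterion 4 already removes men with other conditions that may cause urinary symptoms, so a GP no at PSA ≥2 could be rare. No document gives the unassessed share.

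Much of that stands. A reader might infer that the plan has no breakdown of unassessed men; the documents do not support that, and what is missing is narrower: one direct cross and the bounds. A reader might also infer that the leftover GP-based wording yields a second, materially different primary result; if the protocol is followed, it would hardly change the number.

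The reply does not remove the referral conflict. The subtraction needs GP yes to imply PSA ≥2, which the synopsis and the SAP 2.2 footnote do not state. Nor does any passage say that the primary would be conditional on GP judgement if discretion is used.

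**Conclusion.** The point holds in limited form and should be fixed. The current text gives two answers on whether a man with BPE/BPO ≥3 and PSA ≥2 can be kept from the reference assessment. The primary is always conditional on urologist assessment; where GP discretion is used it is also conditional on GP referral, while the objective names only tool and PSA. No bound or sensitivity analysis covers this. The leftover definitions are a minor consistency error.

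The size is illustrative. It depends wholly on the unassessed share and is nil if that share is nil. At the planning value of 0.50 with 500 assessed, 48 unassessed men would match the stated ±0.044 in the worst case; the 0.68–0.83 scenarios need fewer men but rest on weaker assumptions. A reader might go further and infer that the primary will be overstated. The documents do not show that: they give no rate of GP refusals to refer or of non-attendance, and the direction for non-attenders is unknown.

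**What to change.** 1. Reconcile Protocol 4, Protocol 4.1 including Visit 2, and SAP 2.3 on what leads to urologist referral. The sponsor decides the rule.
2. Align the Protocol synopsis (Analysis), Protocol 8.1 and SAP 2.4 with Protocol 8.4.2 and SAP 7.1.2, and the Protocol 3 progression-risk endpoint with Protocol 8.4.3.
3. In SAP 7.1.2 replace Not Applicable with one supportive table of all BPE/BPO ≥3, PSA ≥2 men, split into GP no, no GP answer, GP yes but not assessed, and urologist-assessed, with worst- and best-case bounds on the primary.
4. Keep the observed-case proportion as primary. Describe it as conditional on urologist assessment and, if GP discretion applies, on GP referral.

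The cost is wording changes, a clarifying change to the protocol text and one table from data already collected. The reported range may become wider or less favourable.

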## **3. PLANNED ANALYSES**

### **3.1. Interim Analyses**

No interim analyses are planned for this study.

### **3.2. Final Analyses**

The final planned primary analyses will be performed after the completion of the following sequential steps:

1. All subjects have either completed, or withdrawn from, the study, as defined in the protocol.
2. All required database cleaning activities have been completed and final database release and database freeze has been declared by Data Management.

The primary database freeze, using standard Data Management practices, will occur after the last subject completes Visit 3. Statistical analysis and reporting will be in terms of this primary database freeze and will be referred to as the 'Final Analysis' or primary 'Statistical Analysis Complete' (SAC).

## 4. ANALYSIS POPULATIONS

No investigational study drug is being administered during this study.

This is a non-randomized, interventional study utilizing a questionnaire-based assessment of men in general practice, therefore the populations are not defined in the traditional sense. The following populations will be used on this study.

Population	Definition / Criteria	Analyses Evaluated
Screened	
 
Comprised of all subjects who are screened for eligibility.
 
	
 
Study Population
 
Efficacy (agreement between BPE/BPO and IPSS)
 

Screened But Not Evaluable	
 
Comprised of all subjects who are screened for eligibility, but do not qualify for the Evaluable Population.
 
	
 
Study Population
 
Safety (Adverse Events Listing)
 

Evaluable	
 
Comprised of all subjects who meet the entry criteria, including a positive IPSS screening result (score <math>\geq 8</math>) and/or a positive BPE/BPO screening result (score <math>\geq 3</math>).
 
	
 
Study Population
 
Efficacy
 
Safety
 

**NOTES** : Please refer to [Appendix 15](#): List of Data Displays which details the population to be used for each display being generated.

### 4.1. Protocol Deviations

Important protocol deviations (including deviations related to study inclusion/exclusion criteria, conduct of the trial, patient management or patient assessment) will be summarized and listed.

#### 4.1.1. Inclusion / Exclusion Criteria Deviations

All inclusion / exclusion criteria deviations which are recorded on the inclusion / exclusion screens of the eCRF will be summarized. The tabular summaries will be in terms of number and percent of Screened But Not Evaluable Subjects violating any criterion and violating each criterion.

Listings of inclusion / exclusion criteria deviations will be produced for Screened But Not Evaluable subjects.

#### 4.1.2. Important Protocol Deviations

Protocol deviations identified during the study will be tracked and reviewed by the study team in accordance with SOP-130050 and the FDC116114 Protocol Deviation Management Plan (PDMP). Prior to the final database lock and data analysis for the clinical study report (CSR), the FDC116114 Study team will determine whether any subjects will be excluded from the summary of important protocol deviations as specified in the reporting and analysis plan. Protocol deviation data entered into the eCRF (InForm) will be extracted and processed as a SAS dataset with identifiers for important protocol deviations. Subjects with important protocol deviations will be summarized and

discussed, and the CSR listings will include a list of important protocol deviations occurring in the study; listings of all protocol deviations will be available for regulators if requested.

- Data will be reviewed prior to freezing the database to ensure all important deviations are captured and categorized on the protocol deviations dataset.
- This dataset will be the basis for the summaries and listings of protocol deviations.

Important Deviations will be summarized and listed for Evaluable subjects. The tabular summary will be in terms of number and percent of subjects with any Important Deviations and with each Important Deviation. Summaries will be output by the eCRF categories for the Evaluable subjects and by the following screening tool categories:  $IPSS \geq 8$ ,  $BPE/BPO \geq 3$ ,  $IPSS \geq 8$  and  $BPE/BPO \geq 3$ , and  $IPSS \geq 8$  or  $BPE/BPO \geq 3$ . The eCRF categories are standardized for this study; examples are provided in the tabular summary shells.

Listings of important protocol deviations will be produced for Evaluable subjects.

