## 6.2. Subject Accountability

Summaries for the following will be produced in terms of total number overall:

- All Screened Subjects
- All Evaluable Subjects

Evaluable subjects include those subjects who met all inclusion and exclusion criteria including a positive IPSS (score $\geq$ 8) and/or BPE/BPO (score $\geq$ 3). Summaries for the Screened and Evaluable subjects will also be presented by country, and separately by country and center.

A summary table will be produced for the screened subjects and will contain the following:

- Number of subjects who were sScreened but not Evaluable
- Number of subjects who were Evaluable

A summary of screened subjects by country, and separately by country and center will also be presented.

A summary table will be produced for the Evaluable subjects and will contain the following:

- All Evaluable Subjects (IPSS $\geq$ 8 or BPE/BPO $\geq$ 3)
- Evaluable Subjects with PSA $<$ 2.0ng/mL
- Evaluable Subjects with PSA $\geq$ 2.0ng/mL
- Evaluable Subjects with Any GP Assessment of BPH
- Evaluable Subjects with GP Assessment of BPH="Yes"
- Evaluable Subjects with GP Assessment of BPH="No"
- Evaluable Subjects with GP Assessment of BPH="Yes" and Urologist Assessment of BPH
- Evaluable Subjects with GP Assessment of BPH="Yes" and Urologist Assessment of BPH="Yes"
- Evaluable Subjects with GP Assessment of BPH="Yes" and Urologist Assessment of BPH="No"
- Evaluable Subjects with GP Assessment of BPH="Yes" and Any Urologist Risk Assessment of BPH Progression
- Evaluable Subjects with GP Assessment of BPH="Yes" and Urologist Risk Assessment of BPH Progression="Yes"
- Evaluable Subjects with GP Assessment of BPH="Yes" and Urologist Risk Assessment of BPH Progression="No"

An overall summary and the data above will also be presented by country, and separately by country and center for the Evaluable subjects.

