### 6.3. Subject Disposition

A subject may withdraw from the study at any time at the investigator's discretion or at the request of the subject.

The reason for study withdrawal is recorded in the eCRF for Evaluable subjects who prematurely withdrew from the study prior to completing Visits 1, 2, and 3. A tabular summary will be produced for number and percentage of subjects prematurely withdrawing from the study, overall and by reason. Additional tabular summaries will be produced by Visit (overall and by reason) for subjects withdrawing from the study. For these summaries, the percentages are calculated using the number of subjects in each of the categories (IPSS $\geq$ 8, BPE/BPO $\geq$ 3, IPSS $\geq$ 8 and BPE/BPO $\geq$ 3, and IPSS $\geq$ 8 or BPE/BPO $\geq$ 3) as the denominators.

Listings will be produced for subject disposition and reason for withdrawal and will include key accountability data including study status, completion or withdrawal date, all visit dates, and the primary reason for premature withdrawal.

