## 8.2. Safety Analyses

### 8.2.1. Overview of Planned Analyses

Safety summaries and analyses are reported in terms of the following data classifications: adverse events, clinical laboratory assessments (urinalysis), total serum prostate specific antigen (PSA), and digital rectal examination (DRE).

All safety analyses will be performed using the Evaluable subjects unless otherwise specified in text or data display shells. Applicable safety analysis and reporting definitions and presentations within “Program Safety Analysis Plan (PSAP, 2016) for GI198745 (dutasteride) and GSK2285985 (fixed dose combination of dutasteride [GI198745] and tamsulosin [GI138525])” are utilized within this RAP, with any deviations noted.

[Table 5](#) provides an overview of the planned adverse event tabular summaries. A list of planned data displays is in [Appendix 15](#): List of Data Displays.

Reference Section 4 (Analysis Populations) and [Appendix 6](#) (Derived and Transformed Data) for supporting definitions on all below subsections.

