This is a non-randomized, interventional study utilizing a questionnaire-based assessment of men in general practice, therefore the populations are not defined in the traditional sense; there will be no Per Protocol population for this study. The analysis population will be All Evaluable Subjects.

In accordance with SOP-130050 and the FDC116114 Protocol Deviation Management Plan (PDMP), a final review of the study deviations will be conducted by members of the internal and external Data Management team in advance of database freeze (DBF).

Below is a list of the deviations which are considered important as per the PDMP and will be summarized in a table by category; a supportive 'by subject' data listing will also be provided.

Deviation Category:

- Informed Consent
- Violation of Inclusion Criteria (Inclusion #)
- Violation of Exclusion Criteria (Exclusion #)
- Not Withdrawn After Developing Withdrawal Criteria
- Excluded Medication, Vaccine, or Device
- Assessment or Time Point Completion
- Failure to Report Safety Events per Protocol

 Deviations pertaining to incomplete and out of window assessments will be reviewed in-stream and assigned importance status during protocol deviation review meetings. Deviations related to missed assessments affecting subject safety will be marked "IMP = Y," deviations not affecting subject safety will be marked "IMP=N."

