**Date of Enrollment**

An Evaluable Subject is a subject that was not a screen failure and also met the IPSS and/or BPE/BPO entry criteria (IPSS  $\geq 8$  and/or BPE/BPO  $\geq 3$ ). The Date of Enrollment is the later of the Screening date and IPSS and BPE/BPO assessment completion dates.

Study Day is calculated as the number of days from the Date of Enrollment:

- Enrollment Date = Missing → Study Day = Missing
- Reference Date < Enrollment Date → Study Day = Reference Date – Enrollment Date
- Reference Date  $\geq$  Enrollment Date → Study Day = Reference Date – (Enrollment Date) + 1

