**11.17. Appendix 17: Amendment 01 Revision**

Item	RAP Revision General Description	RAP Section
01	Indicate RAP "Amendment Number 01" with administrative details including revision number, copyright year, effective date, description, author, and approver.	-Cover page -Document header -Section 1: Key Elements of the RAP -Section 2.1: Changes to the Protocol Defined Statistical Analysis Plan
02	
Redefine the Analysis Populations as follows:
 
Previous: Screened But Not Enrolled Population – Comprised of all subjects who are screened for eligibility but who do not meet the entry criteria.
 
Current: Screened But Not Evaluable Population - Comprised of all subjects who are screened for eligibility, but do not qualify for the Evaluable Population.
 
Previous: Enrolled Population - Comprised of all subjects who meet the entry criteria, including a positive IPSS screening result (score ≥8) and/or a positive BPE/BPO screening result (score ≥3).
 
Current: Evaluable Population - Comprised of all subjects who meet the entry criteria, including a positive IPSS screening result (score ≥8) and/or a positive BPE/BPO screening result (score ≥3).
 
Note: the population definition did not change for the Enrolled/Evaluable Population.
	-Section 1: Key Elements of the RAP -Analysis Populations  -Section 4: Analysis Populations
03	
Remove the following text:
 
Number of subjects who were incorrectly enrolled with IPSS<8 and BPE/BPO<3.
 
This bullet point is no longer needed in this section. This group of subjects will no longer need to appear on the Summary Table for Screened subjects since they will be included with the Number of Screened But Not Evaluable subjects.
	-Section 6.2: Subject Accountability
04	
Update the names of the study populations as follows:
 
Screened But Not Enrolled Population is changed to the Screened But Not Evaluable Population
 
Enrolled Population is changed to the Evaluable Population.
	-Section 4.1.1: Inclusion / Exclusion Criteria Deviations -Section 4.1.2: Important Protocol Deviations -Section 6.1: Overview of Planned Analyses -Table 2: Overview of Planned Study Population analyses

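### Men enrolled in error with both scores negative are pooled with men never enrolled, so they leave the disposition, important-deviation and safety tables, and the score-criterion violation row cannot be filled

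*SAP*

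**What the plan says.** The SAP defines Evaluable in three places.

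- SAP 4: "Comprised of all subjects who meet the entry criteria, including a positive IPSS screening result" (or a positive BPE/BPO result).
- SAP 6.2: "Evaluable subjects include those subjects who met all inclusion and exclusion criteria including a positive IPSS" and/or a positive BPE/BPO score.
- SAP Appendix 6, under Date of Enrollment: "An Evaluable Subject is a subject that was not a screen failure and also met the IPSS and/or BPE/BPO entry criteria".

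Every other screened man falls into Screened But Not Evaluable (SAP 4). SAP Appendix 17 confirms that this is meant to cover men enrolled by mistake with both scores below threshold: "they will be included with the Number of Screened But Not Evaluable subjects". The accountability table for screened men in SAP 6.2 accordingly has only two rows, Screened But Not Evaluable and Evaluable.

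Three groups of displays are then tied to Evaluable.

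- Deviations (SAP 4.1.2): "Important Deviations will be summarized and listed for Evaluable subjects". The categories that count as important, in SAP Appendix 1, include "Violation of Inclusion Criteria (Inclusion" followed by a criterion number, and the matching category for exclusion criteria.
- Disposition (SAP 6.3): "The reason for study withdrawal is recorded in the eCRF for Evaluable subjects who prematurely withdrew".
- Safety (SAP 8.2.1): "All safety analyses will be performed using the Evaluable subjects unless otherwise specified in text or data display shells".

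**The concern.** A man who passed into Part I despite two negative scores was enrolled and may have had study procedures. He differs from a man turned away at screening, but the plan counts the two together. SAP 4.1 undertakes to summarise and list important deviations, eligibility deviations included, and SAP 4.1.2 describes a listing of those that arose in the study. Yet the population chosen for that table is defined by passing the very criterion that was breached.

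The study report could then show no breach of the score criterion among enrolled men even where breaches occurred. It could also leave men who had study procedures out of adverse-event counts and denominators, and say nothing in the disposition tables about what happened to men stopped for ineligibility. Protocol 5 treats eligibility deviations as a threat to the study's integrity, so their frequency should be visible.

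**Working it through.** The plan gives no figure on this point to reproduce, so the check sets the definitions side by side and traces one man through the displays.

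**Inputs.** There are five inclusion criteria (Protocol 5.1) and seven exclusion criteria (Protocol 5.2), so 5 + 7 = 12 possible eligibility-violation rows. Inclusion 5 is the score criterion. Populations for each display come from SAP Appendix 15.

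**Step 1: which rows of Table 1.14 can be non-zero?** Take one man per criterion, enrolled in error and violating only that criterion.

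| Definition of Evaluable | Violators who stay Evaluable | Rows zero by construction |
|---|---|---|
| SAP 4 and 6.2 (all entry criteria met) | 0 of 12 | 12 |
| SAP Appendix 6 (not a screen failure, score criterion met) | 11 of 12 | 1 (inclusion 5) |

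The 11 hold under either description of a screen failure in Protocol 5.3. One requires that the man was not later enrolled; these men were enrolled. The other requires both failed criteria and no qualifying score; these men have a qualifying score. The inclusion 5 row is zero under all three SAP definitions.

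**Step 2: where does the man with two negative scores go?** He is outside Evaluable under every definition, so he is absent from:

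- disposition and withdrawal, Tables 1.11–1.13;
- important deviations, Table 1.14 and Listing 1.5;
- safety summaries, Tables 3.1–3.31;
- fatal, serious and withdrawal adverse-event listings, Listings 3.5–3.7.

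He also fits none of the four score columns in SAP 4.1.2 (IPSS positive, BPE/BPO positive, both, either).

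**Step 3: what procedures could he have had?** SAP 2.3 and the Time and Events Table place the urine strip test, PSA draw and optional GP rectal examination after enrolment at Visit 1.

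**Step 4: where does he still appear?** His failed criterion can appear in Table 1.5 and Listing 1.2, and his adverse events in Listing 3.1. All three cover Screened But Not Evaluable as a whole. Failing inclusion 5 is also the ordinary route to screen failure, so nothing in the planned content separates him from a man never enrolled. Table 1.5 draws on the inclusion/exclusion screens of the eCRF. If the site recorded him as eligible and did not correct the screen (an assumption), he is missing from Table 1.5 as well as Table 1.14.

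**Step 5: efficacy.** The primary denominator requires BPE/BPO of at least 3 (SAP 7.1.2), so he cannot enter it. The kappa analysis uses All Screened Subjects (Tables 2.1–2.3), which is unchanged by how he is classified.

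**Size.** The documents do not say how many such men there are. As an illustration only, assume 1,000 enrolled and 1% to 5% enrolled in error on the score: 1,000 × 0.01 = 10 to 1,000 × 0.05 = 50 men. The inclusion 5 row would read 0 instead of 10 to 50, and safety denominators would be 990 to 950 instead of 1,000.

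**The case against.** The best defence has four parts.

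- **The grouping has some protocol support.** One of the two descriptions in Protocol 5.3 does not mention enrolment: failing the criteria and having no qualifying score is enough. A man negative on both tools fits it. This stands, but it does not make his procedures or his deviation any less reportable.
- **Information is kept elsewhere.** Besides Table 1.5 and Listings 1.2 and 3.1, SAP 11.7.2 says exclusions from summaries will be documented with reasons in the study report, and SAP 4.1.2 makes full deviation listings available to regulators on request. The table shells are filed separately and may flag enrolment status. A reader might infer that these men vanish from the report; the documents do not support that. What is lost is a separate count and their place in the tables.
- **Exposure is slight.** There is no study drug, and Protocol 4.6.1 rates the procedures as minimal risk. A reader might also suppose a urologist's examination. Under Protocol 4, probable BPH needs a positive score together with PSA of at least 2 ng/mL, so a man negative on both tools would reach the urologist only through a further deviation.
- **One restored row would give the frequency.** That is true of the count, but not of dispositions, deviations or adverse events.

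A reader might also conclude that every eligibility row in Table 1.14 must be zero. That follows from SAP 4 and 6.2 but not from SAP Appendix 6, where 11 of the 12 rows can be filled. The firm statement is limited to inclusion 5.

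**Conclusion.** The point holds in a limited form. Men enrolled with both scores negative are pooled with men never enrolled and leave the disposition, important-deviation and safety summaries. The inclusion 5 violation row is zero under every SAP definition of Evaluable. For the other 11 criteria the answer depends on which definition is programmed, and that conflict needs resolving in its own right.

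The conclusion assumes that the separately filed shells do not change the populations in Appendix 15, and that the important-deviation table is broken down by criterion number, as its category label implies. The number of men affected cannot be computed from the documents. The primary proportion is not at risk from men negative on both tools. Severity is minor, because only descriptive reporting is affected.

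**What to change.** 1. Reconcile SAP 4 and 6.2 with SAP Appendix 6 into one definition of Evaluable.
2. Restore a separate enrolled-in-error row in Table 1.1, apart from men who failed screening and were never enrolled.
3. Define an all-enrolled set: any man who passed to Part I or had a post-enrolment procedure. Use it for disposition (Tables 1.11–1.13), important deviations (Table 1.14, Listing 1.5) and adverse events (Tables 3.1–3.22, Listings 3.2–3.9). Add an overall column, since men negative on both tools fit none of the four score columns.
4. Report withdrawal reasons for these men where the eCRF already holds them. SAP 6.3 describes recording for Evaluable men only, so no new collection should be assumed.
5. Keep Evaluable for efficacy.

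The cost is one population flag, one table row, an extra column and slightly larger denominators. No new data are needed and no efficacy result changes.
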